4.2.2 Secondary Efficacy Endpoint

Proportion of patients achieving serologic clearance of HBsAg on Day 169

A patient is considered to have achieved serologic clearance of HBsAg on Day 169, if HBsAg on Day 169 is below the limit of quantitation (defined as 0.05 IU/mL).

Proportion of patients achieving serologic clearance of HBV DNA on Day 169

A patient is considered to have achieved serologic clearance of HBV DNA (PCR) on Day 169, if HBV DNA (PCR) on Day 169 is below the limit of quantitation (defined as 10 IU/mL).

Changes in qHBsAg, HBV DNA, HBcrAg and pg-RNA levels, Baseline to Days 85 and 169
 Changes in qHBsAg, HBV DNA, HBcrAg and pg-RNA levels from Baseline to Days 85 and 169
 are defined as:

Change of Test from Baseline to Day 85 = Test value [Day 85] – Test value [Baseline];

Change of Test from Baseline to Day 169 = Test value [Day 169] – Test value [Baseline];

where Test correspond to the following quantitative tests:

qHBsAg, HBV DNA and HBV DNA log, HBcrAg (Log U/mL and kU/mL) and pg-RNA

• Change in LPMIX9 IFN-γ Spot Forming Cells (SFC) by ELISpot assay in PBMCs, Baseline to Days 85 and 169

Change in LPMIX9 IFN-γ SFC by ELISpot assay in PBMCs, Baseline to Days 85 and 169 are defined as:

Change of LPMIX9 IFN-γ SFC from Baseline to Day 85 = LPMIX9 IFN-γ SFC [Day 85] – LPMIX9 IFN-γ SFC [Baseline];

Change of LPMIX9 IFN-γ SFC from Baseline to Day 169 = LPMIX9 IFN-γ SFC [Day 169] – LPMIX9 IFN-γ SFC [Baseline]

Where LPMIX9 is a pool of the 9 peptides contained in FP-02.2. Values for analyses are LPMIX9 raw values corrected with the control.

- Change in LPMIX9 IFN-γ Spot Forming Cells (SFC) by ELISpot assay in PBMCs:
 - Some replicates of some subjects and days, the -ve Control was higher than the analogous LPMIX9 value which led to negative values.
 - Given that the control does not correspond to the analogous LPMIX9 in each of the replicates since the corresponding wells are not linked, the calculation of the continuous parameter to be analyzed, will be revised as follows:
 - Mean (i=1,2,3) of ["Value for Peptide LPMIX9 (R#i)"] Mean (i=1,2,3) of ["-ve Control for Peptide LPMIX9 (R#i)"] where R#i is replicate #i, i=1,2,3
 - Adding a new specification: If the result turns out negative, it will round up to "0"

Please refer to section 5.3.2 for details on the handling of intercurrent events and missing data or all the secondary endpoints.

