A sentinel cohort of 12 patients (6 receiving HepTcell and 6 placebo) will undergo blinded safety review by the Safety Committee 7 to 10 days after all ongoing patients in the sentinel cohort have completed the respective dose of study medication and will determine the decision to continue at that dose to the expanded cohort. Safety will be assessed in the sentinel cohort before each dose is administered to the expanded cohort. If any of the Stopping Rules in Section 7.1.1 are met in one or more patients and the event(s) is deemed possibly or probably related to HepTcell, dosing will be suspended pending DMC review. DMC recommendations may include instituting modifications to ensure the safety of continued dosing or discontinuing the study. If none of the Stopping Rules are met, randomization and dosing may continue in the expanded study cohort. Patients will be unblinded as necessary to assess the relationship between the study medication and events that meet criteria for Stopping Rules.

Safety laboratory testing (Table 3), including liver panel, for Doses 1 and 2 will be obtained during the visits conducted 7±2 days after these doses of study medication. Safety laboratory testing following Doses 3, 4 and 5 will be obtained in the interval from 7 days after dose administration and before the next dose of study medication is administered. Safety labs after Dose 6 will be assessed at the Day 169 visit. Investigators will review the eligibility of all patients prior to dosing to determine if the next treatment is to be administered. Eligibility for the next treatment will include: 1) confirmation that patients did not meet a Stopping Rule (Section 7.1.1); 2) confirmation that the pre-treatment liver parameters are within acceptable ranges for treatment (below); 3) confirmation that patients do not have a new confirmed or suspected IMC (Appendix 2). Patients not meeting these criteria will not be treated.

If abnormalities of ALT, AST, total bilirubin, direct bilirubin, or international normalized ratio (INR) are reported after dosing is commenced, the following monitoring and dosing rules will be applied:

Toxicity	Management	Discontinuation of Study Medication
ALT or AST \geq 5×but < 10 × ULN, and Total and direct bili < 1.5×ULN, and INR < 1.3 ×ULN	Continue dosing Monitor liver panel weekly If ALT/AST fall to <1.5×ULN, stop weekly monitoring	

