- ^a Randomization may occur up to 3 working days before Day 1 (the day of first dosing) to allow for the possible preparation of study medication by a central pharmacy and shipment to the study site. If the patient is to be randomized before Day 1, the eligibility of the patient will be confirmed by a telephone visit prior to randomization. Concomitant medications AEs will also be assessed.
- b If a patient prematurely discontinues study medication before Day 169, Day 169/Early termination procedures will be performed. Patients who prematurely discontinue study medication will remain in the study for Follow-Up Period study assessments, the dates of visits adjusted to correspond to 13, 26, 39 and 52 weeks after the last dose of study medication.
- ^c A telemedicine visit would include a home visit by appropriate trained personnel to perform a target and symptom-driven physical and obtain vital signs and safety laboratories. The remaining portions of the visit may be conducted virtually by the study investigator.
- d After Day 169 or ET, only immunosuppressive medications, vaccines, and new HBV treatments or medications associated with MAEs, NCIs, SAEs, hepatitis flares, or hepatic injury will be recorded.
- ^e Measured before any blood sample collection.
- f Not required if performed within 12 months or if no fibrosis seen on liver biopsy within 2 years before screening.
- g For women of childbearing potential only. A serum pregnancy test will be obtained in lieu of a urine pregnancy test at screening.
- h Hepatitis B genotyping will be performed at screening if it has not been documented in the prior medical record.
- ¹ Serology and viral markers = HBsAg, anti-HBs, HBVDNA, pg-RNA, HBcAg, HBeAg, HBeAg antibody.
- Jif the patient has experienced an acute illness or temperature > 38°C in the 2 days prior to dosing, the administration of study medication and corresponding visit will be delayed until the illness or fever has resolved.
- k Investigators will review the eligibility of all patients to determine if the next treatment is to be administered. Eligibility for the next treatment will include 1) confirmation that patients did not meet a Stopping Rule (Section 7.1.1); 2) confirmation that the pre-treatment liver parameters are within acceptable ranges for treatment (Section 4.1); 3) confirmation that patients do not have a new confirmed or suspected IMC (Appendix 2). Patients not meeting these criteria will not be treated.

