7. PREMATURE DISCONTINUATION

7.1. Individual Patients

Patients can choose to discontinue study medication or participation in the study at any time, for any reason, without prejudice to their future medical care. Patients could be discontinued for any of the following reasons:

- Patient request/withdrawal of consent
- Noncompliance with study requirements
- Loss to follow-up
- Investigator discretion
- Sponsor request, including termination of the study by the Sponsor

In case of worsening or disease progression, study medication will be discontinued, and the medications prohibited in Section 6.7.1 will be allowed, at the discretion of the investigator and Sponsor, if it is in the patient's best interest to initiate any treatment prohibited in the study.

If a patient prematurely discontinues study medication before Day 169, Day 169/ET procedures will be performed. Patients who prematurely discontinue study medication will remain in the study for Follow-up Period study assessments, with the dates of visits adjusted to correspond to 13, 26, 39 and 52 weeks after the last dose of study medication.

Eligible patients who are randomized and withdrawn before their second dose of study medication will be replaced. Patients who have received two doses of study medication who are subsequently withdrawn from the study will not be replaced.

In consultation with the DMC, patients in the Sentinel Cohort may be replaced at any time to assure that the reliability and integrity of the data from this cohort remains intact.

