10.4. Statistical Methods

10.4.1. Primary Efficacy Endpoint

For the primary analysis, proportions of patients with virologic response, defined as a 1.0-log reduction in HBsAg or serologic clearance of HBsAg, will be compared between HepTcell and placebo groups using Fisher's Exact Test at a 0.05% two-sided level of significance.

Patients who discontinue prematurely or have missing data will be considered nonresponders for that endpoint. Linear and logistic regression will be employed to examine the effects of baseline factors, such as qHBsAg level, HBV DNA levels, and hepatitis B genotype on response.

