10.4.2. Secondary and Exploratory Efficacy Endpoints

The same approach as used for the primary efficacy endpoint will be applied for secondary and exploratory endpoints that are categorical in nature.

Changes from baseline in PBMC ELISpot, HBsAg, HBcrAg, pg-RNA, and quantitative HBV DNA will be analyzed using a mixed model for repeated measures (MMRM). The model will include the fixed effects of treatment, stratification factor, week, and treatment-by-visit interaction as well as the continuous, covariate of baseline level. The model will employ an unstructured within patient covariance matrix and a restricted maximum likelihood (ReML) estimation method.

Relationships between hepatitis flares and HBsAg loss and/or decline will be evaluated logistic and linear regression.

A Kaplan-Meier model will be developed to compare changes between treatment groups in HBsAg clearance and a 1-log reduction in HBsAg over time.

No multiplicity adjustments will be made for secondary or exploratory endpoints.

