5.3.2.2 Secondary endpoints

The secondary efficacy endpoints are related to the evolution of serologic and viral markers as well as the PBMC ELISpot by days 85 and 169.

The secondary endpoints will be considered as described in section 4.2.2. Analyses to be performed are described in the following subsections.

No multiplicity adjustments will be made for secondary endpoints.

5.3.2.2.1 Proportion of patients achieving serologic clearance of HBsAg on Day 169

Patients who discontinue early or have missing HBsAg values on Day 169 but who achieve serologic clearance of HBsAg on the last available assessment prior to Day 169 will be treated as responders for this endpoint; otherwise, patients with early discontinuation or missing HBsAg values on Day 169 will be treated as non-responders.

The proportion of patients achieving serologic clearance of HBsAg on Day 169 will be estimated as follows:

(Number of patients having achieved serologic clearance of HBsAg on Day 169) / (Number of patients in the corresponding treatment (or overall)) x 100%

This proportion will be compared between treatment groups using Chi-Squared Test or Fisher's Exact Test at a 0.05% two-sided level of significance. Fisher's Exact Test will be used if the expected values of at least the 80% of the cells in the contingency table created for estimating proportions are lower than 5.

This proportion will be analyzed using logistic regression models with treatment group and baseline qHBsAg level as covariate. The analysis of maximum likelihood and odds ratio estimates for patients predicting a 'Yes' in achieving serologic clearance of HBsAg on Day 169 will be shown.

5.3.2.2.2 Proportion of patients achieving serologic clearance of HBV DNA on Day 169

Patients who discontinue early or have missing HBV DNA values on Day 169 but who achieve serologic clearance of HBV DNA on the last available assessment prior to Day 169 will be treated as responders for this endpoint; otherwise, patients with early discontinuation or missing HBV DNA values on Day 169 will be treated as non-responders.

The proportion of patients achieving serologic clearance of HBV DNA on Day 169 will be estimated as follows:

(Number of patients having achieved serologic clearance of HBV DNA on Day 169) / (Number of patients in the corresponding treatment (or overall)) x 100%

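### SAP 5.3.2.2.2 scores HBV DNA clearance without regard to new HBV treatment, so a value below 10 IU/mL obtained on an antiviral counts as clearance

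*SAP*

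**What the plan says.** **Definition.** SAP 4.2.2 scores clearance "if HBV DNA (PCR) on Day 169 is below the limit of quantitation (defined as 10 IU/mL", with no condition on treatment. For intercurrent events it points elsewhere: "Please refer to section 5.3.2 for details on the handling of intercurrent events and missing data or all the secondary endpoints".

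**Handling.** SAP 5.3.2.2.2 covers patients who discontinue early or lack a Day 169 value. Those "who achieve serologic clearance of HBV DNA on the last available assessment prior to Day 169 will be treated as responders for this endpoint"; the rest are non-responders. New HBV treatment is not mentioned anywhere in 5.3.2.

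**Protocol rule.** Section 10.4.1 is stricter: "Patients who discontinue prematurely or have missing data will be considered nonresponders for that endpoint". Section 10.4.2 carries it over: "The same approach as used for the primary efficacy endpoint will be applied for secondary and exploratory endpoints that are categorical in nature". Section 10.6 lets the SAP supersede the protocol for everything but the primary analysis. SAP 5.3.17 declares only one change from the protocol, and it concerns ECG parameters.

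**New HBV treatment.** Protocol 6.7.1 and 7.1 allow otherwise prohibited medication on worsening or progression, with study medication stopped. SAP 5.3.1.10 records new HBV treatments as concomitant medication.

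**Sampling.** Protocol Table 1 schedules viral markers at screening, Day 1, Day 85 and Day 169/ET. Its footnote b states: "If a patient prematurely discontinues study medication before Day 169, Day 169/Early termination procedures will be performed". Later visits follow "with the dates of visits adjusted to correspond to 13, 26, 39 and 52 weeks after the last dose of study medication".

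**The concern.** Protocol 1.1.1 describes nucleos(t)ides and interferon as drugs given to suppress viral replication. HBV DNA clearance measures that same effect. A patient who worsens, starts an antiviral and then has HBV DNA below 10 IU/mL shows the action of the antiviral, yet is reported as a response in the assigned arm. The SAP foresees the event, records it and promises a rule for intercurrent events, but the section it points to has none for this one. At stake is the accuracy of the clearance rates in Tables 14.2.2.2.1 and 14.2.2.2.2, both marked for the final report.

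**Working it through.** **The plan's own figure.** The documents give no expected rate or power for HBV DNA clearance. The only stated figure is about 80% power for the primary endpoint (3% against 25%, 40 per arm, two-sided 0.05). Enumerating both binomials with Fisher's exact test gives 78.0%, which agrees. Only the 40 per arm is used below.

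**Route A: ET sample.**
- Stopping study medication triggers ET virology. No text requires that draw to come before the first antiviral dose.
- Under protocol 10.4.1 and 10.4.2 the patient is a non-responder. Under SAP 5.3.2.2.2 the patient is a responder if the ET value is below 10 IU/mL.
- Later follow-up samples do not add to this route. Viral markers are next drawn 26 weeks (182 days) after the last dose. If Dose 1 was the last, that is Day 1 + 182 = 183, or 183 − 10 = 173 with the visit window. This is later than 169 + 2 = 171.

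**Route B: Day 169 sample.**
- *Antiviral started after Dose 6.* No dose is left to discontinue and the Day 169 value is not missing, so it counts as observed. The gap is (169 − 2) − (141 + 2) = 24 days to (169 + 2) − (141 − 2) = 32 days. Worsening would have to be found off schedule, because "Safety labs after Dose 6 will be assessed at the Day 169 visit".
- *Antiviral started while dosing continues or is interrupted.* The bans in protocol 6.7.1 that run through the trial name interferons and other immune-affecting treatments and live vaccines; for HBV agents as a class it bars only prior treatment. Section 6.7 lets the investigator prescribe additional treatment, and the liver rules in 4.1 let dosing be paused and restarted. A nucleos(t)ide start during the dosing period is therefore not clearly barred, and the Day 169 value would again count.

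**Size per patient.** 1/40 = 2.5 points. The number of such patients is not given. Assuming 0 to 3 in one arm, the shift is 0 to 3/40 = 7.5 points.

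**Effect on the test, from equal arms.** Assume b clearances out of 40 in each arm, b = 1 to 12, and add k to one arm. The chi-square test (no correction) uses z = (k/40) / √[p̄(1 − p̄)(2/40)], with p̄ = (2b + k)/80.

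| k | Chi-square p | Fisher p |
|---|---|---|
| 1 | 0.56 to 0.81 | 1.0 |
| 2 | 0.30 to 0.63 | 0.62 to 0.81 |
| 3 | 0.17 to 0.48 | 0.36 to 0.64 |

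The smallest k that reaches p < 0.05 at b = 1, 4, 8 and 12 is 5, 7, 9 and 9 by chi-square, and 7, 8, 10 and 10 by Fisher.

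**Effect on the test, near the boundary.** With 8 of 40 in one arm, one extra clearance in the other can cross 0.05:
- Fisher: 8 against 17 gives p = 0.053; 8 against 18 gives p = 0.031.
- Chi-square: 8 against 16 gives p̄ = 24/80 = 0.30, z = 0.200/√(0.30 × 0.70 × 0.05) = 1.95, p = 0.051. For 8 against 17, p̄ = 25/80 = 0.3125, z = 0.225/√(0.3125 × 0.6875 × 0.05) = 2.17, p = 0.030.

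**The case against.** **The ET route does have a rule.** Treating worsening means stopping study medication, and SAP 5.3.2.2.2 covers early discontinuation. This is fair: on that route the rule is too generous rather than absent. It still gives the wrong answer for a patient on an antiviral.

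**Restoring the protocol's non-responder rule would be simpler.** It would close the ET route, but not the Day 169 route after Dose 6. It would also reclassify discontinuers who never took an antiviral, which is a wider question.

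**Mitigation is already planned.** SAP 5.3.2 plans supportive analyses in the per-protocol population, which requires full dosing and so drops ET patients. However, Appendix 1 lists the clearance tables for mITT only, and a patient who starts an antiviral after Dose 6 stays in the per-protocol set. Listings 16.2.4.5 and 16.2.6.1 read together would identify each case, but the response tables would still count it.

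**Counting the value regardless of rescue is a recognised choice.** It is hard to defend when the rescue drug acts directly on the measured marker, and the SAP does not state that choice.

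**HBsAg could be affected too.** The HBsAg rules have the same silence, and protocol 10.2 attributes a 1.3-log fall at 24 weeks to interferon. Against that, protocol 1.1.1 says nucleos(t)ides rarely achieve HBsAg loss. The documents neither show a material effect on HBsAg nor exclude one, so this point is confined to HBV DNA.

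**Conclusion.** The gap is real and small. As written, the SAP counts an on-antiviral HBV DNA value below 10 IU/mL as clearance. The ET route exists because the SAP loosened the protocol's rule without declaring it.

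Three stronger readings are tempting, and the documents support none of them:
- *That exposure is confined to ET samples and the 24 to 32 days after Dose 6.* The text does not clearly bar a nucleos(t)ide start during dosing or a pause, so that gap does not bound time on antiviral in general.
- *That the test result cannot change.* This is shown only from equal arms with 1 to 3 extra clearances; near 0.05 a single patient can matter.
- *That the trial's result is distorted, or tilted towards HepTcell.* No count of rescued patients is given, it may be zero, and either arm could have more of them. SAP section 2 reports that the primary and secondary endpoints were not met and the study was terminated, so the overall conclusion is unlikely to change.

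The size, 2.5 points per patient, assumes 40 per arm. The range up to 7.5 points and the starting counts of 1 to 12 are assumptions. How quickly an antiviral brings HBV DNA below 10 IU/mL is also not given.

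**What to change.** Add to SAP 5.3.2.2.2: *A patient who starts a new HBV treatment before the HBV DNA sample used for this endpoint is a non-responder, whatever the value; this overrides the last-available-assessment sentence.* Because the rule compares the treatment start date with the sample date, it covers both routes.

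List the rule in SAP 5.3.17 as a post hoc change, since the Week 24 results are already known. Footnote the number of such patients per arm in Tables 14.2.2.2.1 and 14.2.2.2.2. If it is zero, say so; nothing more is needed.

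The cost is one sentence and one flag built from medication start dates and virology sample dates already collected. The downside is a slightly lower response count if anyone was rescued.
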